10.3.5 Safety

All clinical safety data will be summarized by subject and time point as appropriate.

All AEs captured in the database will be listed in by-subject data listings. However, only study product use-emergent AEs will be summarized. A study product use-emergent AE is defined as an AE that is starting or worsening at the time of or after the first study product use.

Frequencies of subjects with study product use-emergent AEs, regardless of relationship to study product, will be summarized and sorted by system organ class. Frequencies of subjects with study product use-emergent serious AEs will be likewise summarized. Frequencies of study product use-emergent AEs will be summarized by severity and relationship to study product.

All concomitant medications recorded will be listed by subject.

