### **8.10.2. Adverse Events**

An AE is any untoward medical occurrence associated with the use of the study product, whether or not considered study product-related. An AE can therefore be any unfavorable and unintended sign (including an abnormal laboratory finding), symptom, or disease temporally associated with the use of a study product, whether or not related to the study product.

Adverse events will be coded using the Medical Dictionary for Regulatory Activities (MedDRA) coding dictionary version 22 or higher.

AEs will be reported under the product last used when the onset of AE occurred or when the severity of an existing AE changes.

Statistical Analysis Plan  
Protocol No.: Fontem-PK-01

The following AE summaries will be presented.

- Overall Summary of AEs: the number of events, number and percent of subjects who experienced AEs, SAEs, severe AEs, related AEs, and AEs leading to study discontinuation; summarized by study product and overall.
- Incidence of AEs by MedDRA SOC and PT: AEs will be summarized by SOC and PT. If a subject has more than one occurrence of the same PT, then the PT will be counted only once for that subject under the SOC in which it was categorized.
- Incidence of AEs by PT and maximum severity will be presented for each level of severity by PT and product use. When a subject experiences the same AE (PT) at more than one level of severity, only the most severe one will be counted.

Additionally, listing of AEs will be presented including all data collected in the CRF, along with the derived variable, duration of AE, and the coded variables, SOC and PT.

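### SAP 8.10.2 lets an adverse event that is improving be reported under a later product; the attribution rule should refer to worsening only

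*SAP*

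**What the plan says.** The attribution rule is one sentence in SAP section 8.10.2: "AEs will be reported under the product last used when the onset of AE occurred or when the severity of an existing AE changes". The clause at issue, "or when the severity of an existing AE changes", sets no direction for the change in severity. It also does not say whether the event then leaves its first product or appears under both.

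Protocol section 10.3.5 summarises only use-emergent AEs, each being "an AE that is starting or worsening at the time of or after the first study product use". SAP section 2 says the SAP's analyses take precedence over the protocol's outline, and SAP section 9 lists no changes.

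Three AE summaries follow in SAP section 8.10.2:
- The overall summary gives numbers of events and of subjects, by study product and overall.
- In the table by system organ class (SOC) and preferred term (PT), if a PT recurs in a subject, "then the PT will be counted only once for that subject under the SOC in which it was categorized". No product split is named for this table.
- The severity table is described thus: "Incidence of AEs by PT and maximum severity will be presented for each level of severity by PT and product use". Where one PT occurs at several grades in a subject, "only the most severe one will be counted".

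Neither counting rule states whether it applies within a product or across the study.

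**The concern.** Each subject is scheduled to use six products in turn, so the attribution rule decides which column of the safety tables an event enters. Easing is a change in severity. A programmer who follows the sentence as written would place a resolving event under whichever product happened to be used before it eased. That product did not start the event or make it worse.

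The order of use gives the problem a direction. The usual-brand cigarette (Product F) is used at Visit 2 by everyone, and only the order of Products A to E is randomised, over Visits 3 to 7. Between scheduled sessions, an event that began after F can be carried only into an e-cigarette column, and no scheduled session of F follows to receive one. Evaluating e-cigarette safety is a stated secondary objective, and the AE tables are part of the evidence for it, together with heart rate and blood pressure.

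**Working it through.** Neither document gives an AE rate, an AE duration or a power calculation, so there is no planned figure to reproduce. The check is a worked case, then the size of one misplacement, then an illustration under stated assumptions.

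**1. Worked case.** Suppose a moderate headache starts after F at Visit 2, is still present when the first e-cigarette is used, and then eases to mild.
- Onset clause of SAP 8.10.2: report under F.
- Severity-change clause of SAP 8.10.2: the grade changed when the e-cigarette was the latest product, so report under the e-cigarette.
- Criterion of Protocol 10.3.5, applied to the e-cigarette: the event neither started nor worsened there, so nothing is counted.

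If the SAP means that a record is added, the counts are F = 1 and e-cigarette = 1. If it means that the record moves, they are F = 0 and e-cigarette = 1. The e-cigarette gains a count on both readings.

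**2. Size of one misplacement.** Inputs: 20 subjects (Protocol section 5.2), each using six products.
- Later product: 1/20 = 5 percentage points up.
- Onset product: unchanged if a record is added; 5 points down if the record moves. In the second case the difference between the two products shifts by 5 + 5 = 10 points.
- Nothing changes in the later product's subject incidence if that subject already has a separate occurrence of the same PT there.
- If both alternates allowed by Protocol section 5.2 smoke at Visit 2 and so enter the Safety Population, and that whole population is the denominator, the step is 1/22 = 4.5 points.

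**3. Illustration, on assumptions only.** Let *p* be the chance that a given PT starts after a product, the same for every product and independent between products. Let *q* be the share of such events still open at the next product use that then improve. With a record added, the apparent e-cigarette rate is *p* + (1 − *p*)·*p*·*q*. The expected extra subject-product counts over the five e-cigarettes are 5 × 20 × (1 − *p*)·*p*·*q*.

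| *p* | *q* | Apparent rate, A to E | Extra counts over five products |
|---|---|---|---|
| 10% | 5% | 10.45% | 0.45 |
| 10% | 10% | 10.9% | 0.9 |
| 10% | 20% | 11.8% | 1.8 |
| 20% | 5% | 20.8% | 0.8 |
| 20% | 10% | 21.6% | 1.6 |
| 20% | 20% | 23.2% | 3.2 |

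The apparent rate for F stays at *p*. The relative inflation is 4% to 18%. Under the worsening-only rule the extra counts from improvement are zero.

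**4. The counting rules.** Applied within product, the expected number of subject-product counts for a PT is 20 × 6 × *p*, and none is lost. Applied across the whole study it would be 20 × [1 − (1 − *p*)^6]:
- *p* = 5%: 6.0 falls to 5.3 (11.7% fewer).
- *p* = 10%: 12.0 falls to 9.4 (21.9% fewer).
- *p* = 20%: 24.0 falls to 14.8 (38.5% fewer).

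This shows only why the intended scope is worth writing down. It is not evidence that the across-study reading is intended.

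**The case against.** Several points on the other side are sound.

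- **The two rules do different jobs.** Protocol 10.3.5 defines which AEs are summarised, relative to the first product use of the study. It does not allocate events between products. This stands, so the SAP sentence is out of line with the protocol's principle and does not break a rival attribution rule. It does not explain why improvement should assign an event to a product.
- **The SAP does not say that the record moves.** It may mean an additional record, in which case the onset product keeps its event. This stands, and transfer cannot be asserted as fact.
- **Easing may never create a new severity entry.** Protocol section 9.15.1.2 asks for a severity for each event and has a separate outcome field that includes improvement. The documents do not settle this. But the SAP rule operates on changes in severity, so it presupposes that they are captured.
- **The direction is not absolute.** A reader might infer that events from F can be charged only forward, to e-cigarettes. Protocol section 4.3.4 allows usual-brand smoking during the at-home familiarization day, so F could be the product last used between visits if home smoking counts as use. The one-way claim holds only between scheduled sessions.
- **Once-per-subject counting is normal.** A reader might infer that the PT rules delete real recurrences from all products but one. The text does not support that. Counting a PT once per subject is the standard rule for subject incidence, the severity table is laid out by product, the overall summary gives event counts by product, and the listings keep every record. At most, the words limiting the rule to each product are missing.
- **It may be rare.** The event must last until the next product is used, with visits at least 2 days apart though home use may come sooner, and then change grade. AE reporting is descriptive, with no test resting on it.

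**Conclusion.** The point holds for the attribution rule. As written, SAP 8.10.2 allows an AE that is improving to be reported under a later product, which departs from the starting-or-worsening principle of Protocol 10.3.5 without being declared in SAP section 9. Between scheduled sessions the effect would fall mainly on the e-cigarettes.

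The firm figure is 5 percentage points per affected subject on a denominator of 20, provided the subject has no other occurrence of that PT under the same product. The total effect cannot be estimated from the documents. The illustrative 0.45 to 3.2 extra counts rest on assumed values of *p* and *q*.

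A reader might go further and conclude that the by-product AE rates are wrong in both directions. That is not established. The upward error needs an event that spans two products and then eases. A downward error needs either the reading in which a record moves or the across-study reading of the counting rules, and the SAP states neither. The counting rules need a clarification, not a correction.

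**What to change.** In SAP section 8.10.2:

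1. Replace *changes* with *worsens* in the attribution sentence.
2. State that an AE that improves is reported under its onset product only.
3. State that an AE that worsens stays under its onset product and is also counted under the product last used when it worsened.
4. As a clarification, add *within each study product* to the once-per-PT rule and to the maximum-severity rule, and keep once-per-subject counting for the overall column.

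The cost is a few words in the SAP and a product key in the AE program. No additional data are needed.

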#### **8.10.3. Laboratory Tests**

Clinical biochemistry, hematology, and urinalysis laboratory results from screening visit will be listed.

#### **8.10.4. Vital Signs**

Vital signs (systolic and diastolic blood pressure and pulse rate) will be summarized descriptively by time point. Change from baseline values will be calculated and summarized similarly.

### **8.11. OTHER DATA**

Other data including urine drug screen, urine cotinine, pregnancy test, expired carbon monoxide breath test, and randomization data will be listed.

## **9. CHANGES TO THE PLANNED ANALYSES**

None.

Statistical Analysis Plan  
Protocol No.: Fontem-PK-01

## 10. SAP APPENDICES

### APPENDIX 1 STUDY EVENTS FLOW CHART

	Screening Visit 1	Product use phase (Visits 2 to 7)	Follow-up phone call/visit
Informed consent	X		
Socio-demographic data	X		
Biochemistry, hematology, and urinalysis	X		
Urine drugs of abuse screen	X		
Urine cotinine level (must be >200 ng/mL)	X		
Alcohol breath test	X		
Inclusion/exclusion criteria	X	X	
Urine pregnancy test 	X	X	
Electrocardiogram 	X	X	
Prior/concomitant medications	X	X	X
COVID-19 screening 	X	X	
SARS-CoV-2 (coronavirus) rapid (10 minute) antigen test	X		
Nicotine use history 	X		
Exhaled carbon monoxide level (must be >10 ppm)	X		
Medical history	X		
Vital signs, height, and weight 	X		
Study product trial use session	X		
Randomization		X (Visit 2 only)	
Test product use			
At-home familiarization period 		X 	
Compliance check 		X	
Blood draws for nicotine pharmacokinetics		X 	
Heart rate and blood pressure measurements		X 	
Product liking, urge to smoke, intent to use product again questionnaires, and Product Evaluation Scale (PES)		X	
Puff topography assessments		X	
Mass change measurements		X	
Adverse events		X	X
Post-study assessments			
Telephone call to subjects 			X
Safety assessments (vital signs, biochemistry, hematology, and urinalysis) and physical exam 			X

Female subjects of child-bearing potential, at Visit 1 and before any product use.

Single 12-lead ECG will be taken following resting in the supine position for at least 5 minutes.

Subjects will be queried for symptoms of COVID-19 at each encounter (both in person and telephone reminder calls for visits). In addition, at each study site visit, body temperature will be assessed before allowing the subject to enter the clinic. If the subject has a COVID-19 vaccination card, a copy of it will be obtained for the subject's study record; however, being vaccinated is not a requirement to enter the study.

Fagerström Test for Nicotine Dependence and nicotine use history questionnaires.

Blood pressure and heart rate.

Subjects must abstain from any nicotine-containing products for at least 12 hours prior to product use visits.

The day prior to their study site visit to use that product; for blu disposable only.

Exhaled CO <15 ppm.

-5, 3, 5, 7, 10, 15, 20, 30, 45, 60, 90, 120, 135, 150, 165, and 180 minutes.

Before any product use; during and after product use sessions.

Between 5 and 7 days after the last study site visit.

Symptom driven, if indicated and requested by the study physician following post-study telephone call.

## APPENDIX 2            QUESTIONNAIRES

### APPENDIX 2.1        NICOTINE USE HISTORY QUESTIONNAIRE

1. Do you currently smoke cigarettes? Yes  No  (If no, exclude)
  
2. If yes:
  - a. Average number of cigarettes smoked per day during the past 3 months? 
    - i. What brand do you smoke?  menthol or tobacco flavor?
    - ii. Full flavor  Medium  Light  Ultralight
    - iii. Filter  Non filter
    - iv. Commercially rolled  roll your own  (exclude if roll your own)
  
3. Age started smoking?
  
4. Maximum CPD smoked on average during any one year since started smoking?
  
5. Have you used any nicotine containing products other than cigarettes or e-cigarettes in the past 14 days?
  - a. No  Yes  (exclude if yes)
  
6. Number of serious quit attempts?
  
7. If >0:
  - a. Longest time quit smoking? Years  Months  Days
  - b. Methods used to quit smoking:
    - i. Counseling Yes  No
    - ii. Nicotine gum Yes  No
    - iii. Nicotine lozenge Yes  No
    - iv. Nicotine patch Yes  No
    - v. Nicotine inhaler Yes  No
    - vi. Nicotine nasal spray Yes  No
    - vii. Chantix Yes  No
    - viii. Zyban Yes  No
    - ix. Electronic Cigarette Yes  No
  - c. Did you use an electronic cigarette in your most recent attempt to quit smoking? Yes  No
  
8. Length of time you have used the following types of electronic cigarettes?
  - a. Cigalike: Years  Months  Days  Never used
  - b. Cartridge/Pod type: Years  Months  Days  Never used
  - c. Vape pen: Years  Months  Days  Never used
  - d. Large tank: Years  Months  Days  Never used

Statistical Analysis Plan  
Protocol No.: Fontem-PK-01

e. Mod unit: Years \_\_\_\_\_ Months \_\_\_\_\_ Days \_\_\_\_\_ Never used \_\_\_\_\_

9. Are you currently using (within the past 7 days) any of the following types of electronic cigarettes:

- a. Cigalike: Yes \_\_\_\_\_ No \_\_\_\_\_
- b. Cartridge/Pod type:: Yes \_\_\_\_\_ No \_\_\_\_\_
- c. Vape pen: Yes \_\_\_\_\_ No \_\_\_\_\_
- d. Large tank: Yes \_\_\_\_\_ No \_\_\_\_\_
- e. Mod unit: Yes \_\_\_\_\_ No \_\_\_\_\_

10. Use of other tobacco products. Have you ever used:

- a. Chewing tobacco Yes \_\_\_\_\_ No \_\_\_\_\_
- b. Pipe Yes \_\_\_\_\_ No \_\_\_\_\_
- c. Hookah Yes \_\_\_\_\_ No \_\_\_\_\_
- d. Small Cigar Yes \_\_\_\_\_ No \_\_\_\_\_
- e. Large Cigar Yes \_\_\_\_\_ No \_\_\_\_\_
- f. Snus Yes \_\_\_\_\_ No \_\_\_\_\_

**APPENDIX 2.2 FAGERSTRÖM TEST FOR NICOTINE DEPENDENCE**

1. How soon after you wake up do you smoke your first cigarette? (Check one)	Within 5 minutes  6-30 minutes  31-60 minutes  After 60 minutes 
2. Do you find it difficult to refrain from smoking in places where it is forbidden, e.g., in church, at the library, in cinema, etc.? (Check one)	Yes  No 
3. Which cigarette would you hate most to give up? (Check one)	The first one in the morning  Any other 
4. How many cigarettes/day do you smoke?	10 or less  11-20  21-30  31 or more 
5. Do you smoke more frequently during the first hours after waking than during the rest of the day?	Yes  No 
6. Do you smoke if you are so ill that you are in bed most of the day?	Yes  No 

## Statistical Analysis Plan

## APPENDIX 2.3

## PRODUCT LIKING QUESTIONNAIRE

Please indicate on the line below how much you liked the combustible cigarette/e-cigarette you have just used.

Not at all  A great deal

## Appendix 2.4 Urge To Smoke Questionnaire

How strong is your current urge to smoke your usual brand cigarette?

For more information, contact the Office of the Vice President for Research and Economic Development at [contact] or [[contact]](mailto:[contact]).

No Urge

## Very Strong Urge

## APPENDIX 2.5 Intent To Use Product Again Questionnaire

How likely are you to use the cigarette/e-cigarette you have just used in the future?

For more information, contact the Office of the Vice President for Research and Economic Development at [contact] or [[contact]](mailto:[contact]).

Definitely would not

### Definitely would

**APPENDIX 2.6      Product Evaluation Scale Questionnaire**

	1 Not at all	2 Very Little	3 A little	4 Moderately	5 A lot	6 Quite a lot	7 Extremely
1. Was it satisfying?							
2. Did it taste good?							
3. Did you enjoy the sensations in your mouth?							
4. Did it calm you down?							
5. Did it make you feel more awake?							
6. Did it make you feel less irritable?							
7. Did it help you concentrate?							
8. Did it reduce your hunger for food?							
9. Did it make you dizzy?							
10. Did it make you nauseous?							
11. Did it immediately relieve your craving for a cigarette?							
12. Did you enjoy it?							
13. Did it relieve withdrawal symptoms?							
14. Did it relieve the urge to smoke?							
15. Was it enough nicotine?							
16. Was it too much nicotine?							
17. Was it easy to use?							
18. Were there bothersome side effects?							
19. Were you comfortable using the product in public?							
20. Did you still have a craving for a cigarette after using the product?							
21. Are you concerned that you would become dependent on this product?
